4. TRIAL DESIGN

4.1 Efficacy endpoints

The primary efficacy endpoint will be the incidence of the requirement for endotracheal intubation and instillation surfactant to “usual care” over 72 hours, the time course for acute RDS.

Secondary efficacy endpoints will measure other clinical parameters that are indicative of lung surfactant sufficiency:

- (a) Incidence of death and/or bronchopulmonary dysplasia (defined as an oxygen requirement to maintain acceptable blood oxygen saturations) at 28 days or discharge, whichever comes first.
- (a) Severity of acute RDS measured by quantitation of oxygen supplementation and respiratory support from randomization to 72 hours of age or intubation and surfactant instillation, whichever comes first.
- b) Duration of acute RDS measured by duration of supplemental oxygen.
- c) Protection from acute lung injury as measured by the incidence of lung air leaks or pulmonary hemorrhage from randomization to 72 hours of age or intubation and surfactant instillation.

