6.3 Subject Compliance No compliance concerns for NICU patients

7. ASSESSMENT OF EFFICACY OF AEROSOLIZED INFASURF

7.1 Parameters

- 1) Comparison of requirement for instilled surfactant to "usual care" over 72 hours.
- 2) Comparison of severity of RDS to "usual care" over 72 hours.
- 3) Comparison of duration of respiratory support for RDS to "usual care" up to 7 days.
- 4) Comparison of incidence of pulmonary complications of RDS to "usual care" to 7 days.

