7.2 Efficacy methods

All data will be extracted from each patient's medical record and entered into a case report form. No specific testing is defined. Data to be extracted to assess efficacy is:

- 1) Requirement for Instilled Surfactant to 72 hours of age.

- Number of patients requiring surfactant instillation from randomization to 72 hours of age. Intubation and instillation is indicated if there is a continuing, > 1hour, requirement for >40% inspired oxygen plus continuing positive pressure support to maintain acceptable blood oxygen saturations.

2) Measures of Severity of RDS from Randomization to Surfactant Instillation or 72 hours of age.

- (a) Supplemental oxygen measured as the increase and/or decrease over time.
- (b) Duration of positive pressure respiratory support over time.

3) Duration of RDS to 7 days of age :

- (a) Time from birth to when patient last required >25% oxygen.
- (b) Requiring >25% oxygen for ≥7 days (168 hours) from birth shall be defined as “unresolved RDS”.

4) Incidence of pulmonary complications to 7 days of age

- (a) Occurrence(s) of radiologically or clinically diagnosed pneumothorax, pneumomediastinum, pulmonary interstitial emphysema, subcutaneous emphysema or pneumopericardium.
- (b) Pulmonary hemorrhage defined as gross bleeding from the airway, changes in a chest X-ray consistent with pulmonary hemorrhage and acute deterioration of respiratory function.
- (c) Acute pneumonia defined as acute deterioration of respiratory function accompanied by clinical and chest X-ray findings consistent with bacterial pneumonia and a clinical decision to institute appropriate antibiotic therapy for acute pneumonia.

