Secondary analyses. Secondary efficacy outcomes representing measures of severity of RDS (oxygen supplementation and respiratory support measures from randomization to Surfactant Instillation or 72 hours of age, whichever comes first) will be summarized using standard descriptive statistics and compared between treatment groups using the stratified Wilcoxon rank sum test. In the case of outcomes measuring the duration of acute RDS (duration of supplemental oxygen), so to accommodate the potential censoring involved, distributional estimates will be based on the Kaplan-Meier method and groups differences statistically assessed using the stratified log-rank test. For the comparison of measures of protection from acute lung injury (incidence of lung air leaks or pulmonary hemorrhage from randomization to 72 hours or intubation and surfactant instillation), the Cochran-Mantel-Haenszel test will be used. All statistical tests will be one-sided and tested at a 5% nominal significance level.

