9.2 Sample size justification

In order to gauge the adequacy of the proposed sample size, the statistical power based on the proposed superiority analyses described above was determined. Power in this context is defined as the probability of deeming the experimental treatment superior to active control after performing the test for superiority on the study data at the conclusion of the study, done in conjunction with a 5% nominal significance level. For the sake of simplicity, calculations corresponding to the test based on the proposed approach are approximated by those of a simple two-sample binomial test. We assume the intubation probability corresponding to the active control group to be 60%. This is based on an abstract presented at the Pediatric Academic Societies meeting of 2016 in which the incidence of intubation and instillation of surfactant among infants with early RDS requiring 30 - 40% oxygen was 32 of 50, 64%. A clinical meaningful effect in the uninstalled cohort is defined as a 20% decrease (in percentage points) in the intubation rate which equates to a 48% intubation rate. Calculations show a sample size of 229 per group (458 total) in this cohort will result in a test procedure which is associated with power of approximately 80.1%. In the post-instilled cohort, 200 subjects will be enrolled. This will provide approximately 80% power is detecting a 30% decrease in the intubation rate (60% versus 42%).

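### Duration of positive-pressure support is cut off at surfactant instillation, the primary failure event, with no rule for instilled infants, so an early failure ranks better than a success weaned later

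*Combined protocol and SAP*

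**What the plan says.** Three sections set the same window for RDS severity. Section 4.1 defines it by "quantitation of oxygen supplementation and respiratory support from randomization to 72 hours of age or intubation and surfactant instillation, whichever comes first". Section 7.2 item 2 is headed "Measures of Severity of RDS from Randomization to Surfactant Instillation or 72 hours of age", and its item 2(b) is "Duration of positive pressure respiratory support over time". Section 9.1 repeats the window ("oxygen supplementation and respiratory support measures from randomization to Surfactant Instillation or 72 hours of age, whichever comes first") and assigns the stratified Wilcoxon rank sum test, one-sided at 5%.

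No section gives an instilled infant a rank, score or censoring rule on these measures. Kaplan-Meier and log-rank methods are reserved for duration of supplemental oxygen, and 9.4 rules out imputation.

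Section 7.1 item 3 lists "Comparison of duration of respiratory support for RDS to" usual care up to 7 days. Section 7.2 item 3 then defines duration only through oxygen: "Time from birth to when patient last required >25% oxygen". Section 9.1 assigns no test to duration of support beyond the truncated window.

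The planning rates are in 9.2: "We assume the intubation probability corresponding to the active control group to be 60" percent, with a target in the uninstilled cohort "which equates to a 48% intubation rate" and 42% in the post-instilled cohort.

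**The concern.** For a duration, shorter is better. If counting stops when treatment fails, failure itself produces a short, good-looking value. The event that stops the clock is the one aerosol is meant to prevent, so the arms are planned to differ in how many infants are cut off. Each avoided instillation replaces a time to rescue with a time to weaning. Whether that helps or hurts the aerosol arm depends on which of the two is usually longer, not on whether infants spend less time on support. A true benefit could be masked or reversed, and earlier rescue on aerosol would be scored as an improvement.

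This does not apply to FiO2 level or change before rescue, for which the same window is reasonable.

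**Working it through.** **1. The plan's own figure.** The documents give no figure for this measure. The primary power in 9.2 reproduces with a one-sided 5% continuity-corrected two-sample binomial test: 229 per arm, 0.60 vs 0.48, null SE = √(2×0.54×0.46/229) = 0.0466, alternative SE = √((0.24+0.2496)/229) = 0.0462. Power = Φ[(0.12 − 1/229 − 1.645×0.0466)/0.0462] = 80.1%. For 100 per arm and 60% vs 42%, power is 78.0% with the correction and 82.0% without, which brackets the stated 80%. The planned rates and sizes are therefore used below as they stand.

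**2. Share cut off.** With 1:1 allocation: (0.60+0.48)/2 = 54% uninstilled; (0.60+0.42)/2 = 51% post-instilled.

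**3. The mis-ranking.** This needs no assumption about the distribution of times. An infant instilled 4 h after randomization contributes at most 4 h. One never instilled and weaned at 30 h contributes 30 h. The failure gets the better rank.

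**4. What the Wilcoxon test then measures.** Let π be the chance that a random rescue comes sooner after randomization than the weaning of a random never-instilled infant (not in the documents). Assume the same rescue and weaning times in both arms. The chance that an aerosol infant scores better than a control infant is

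θ = pA(1−pC)π + (1−pA)pC(1−π) + 0.5[pA·pC + (1−pA)(1−pC)].

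- Uninstilled (pA 0.48, pC 0.60): 0.192π + 0.312(1−π) + 0.248 = 0.56 − 0.12π.
- Post-instilled (pA 0.42, pC 0.60): 0.168π + 0.348(1−π) + 0.242 = 0.59 − 0.18π.

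**5. How often the test favours aerosol.** Approximately Φ[(θ − 0.5)/SD − 1.645], where SD = √((2n+1)/(12n²)): 0.0270 at 229 per arm and 0.0409 at 100 per arm. For exponential times, π = weaning mean/(rescue mean + weaning mean).

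| Assumed mean rescue / weaning (h) | π | θ, uninstilled / post-instilled | Test favours aerosol |
|---|---|---|---|
| 12 / 36 | 0.75 | 0.470 / 0.455 | 0.3% / 0.3% |
| 24 / 24 | 0.50 | 0.500 / 0.500 | 5% / 5% |
| 36 / 12 | 0.25 | 0.530 / 0.545 | 30% / 29% |

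Simulation (unstratified, because the number of centers is not given; no deaths) agrees. Confining rescues and support to an assumed 60 to 66 h after randomization leaves the first row near 0%, lowers the second to 3% to 4% and lowers the third to 21% to 24%. If instilled infants are ranked worst and tied, the test favours aerosol in about 76% to 79% in every row, because that rule credits the primary effect itself.

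**6. Earlier rescue on aerosol.** Assume 60% instilled in both arms, mean rescue 12 h on control and mean weaning 36 h.

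- All aerosol rescue times halved to a mean of 6 h: θ = 0.36×(12/18) + 0.24×(36/42) + 0.24×0.25 + 0.16×0.5 = 0.586. The test favours aerosol in about 94% (229 per arm) or 67% (100 per arm).
- Only 5% of aerosol rescues immediate (0.5 h): about 11% or 8%.
- 10% immediate: about 20% or 14%.

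**7. Air-leak windows, side by side.** Section 4.1(c) and 9.1 count air leaks and pulmonary hemorrhage to 72 hours or instillation, and 9.1 tests that version by Cochran-Mantel-Haenszel. Sections 7.1 item 4 and 7.2 item 4 count the same events, plus acute pneumonia, to 7 days with no stop at instillation and no assigned test.

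**The case against.** The strongest defence is that severity before rescue is a legitimate target: it keeps instilled surfactant out of the comparison and suits objective (b), acute improvement in respiratory function. That stands for oxygen level and change. It does not stand for a duration that becomes shorter because treatment failed.

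Section 9.1 also says that a detailed SAP will follow. But 9.1 has already fixed the window and the test, and a SAP that follows it inherits the problem.

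It can be said that longer support duration is planned: 7.1 item 3 lists it to 7 days, and the respiratory support data sheet records times on and off support. That narrows the gap but does not close it, since 7.2 item 3 defines duration by oxygen alone and 9.1 assigns support duration no test.

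A reader might infer that the rule is biased against aerosol. The documents give no rescue or weaning times, so the direction is open. A reader might also infer that harm would usually be scored as benefit. The 94% figure needs every rescue time halved; section 2.3 reports no discontinuation for interference with breathing in over 30 pilot patients, and adverse events during aerosolization are captured and reviewed under 8.1 and 4.6. Finally, the air-leak texts might be read as two rival definitions of one endpoint. The outcome sets overlap but are not identical, and a tested 72-hour endpoint beside a wider 7-day extraction is a possible reading.

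**Conclusion.** The point holds for one measure within one secondary endpoint and should be fixed. Followed exactly, the plan scores early treatment failure as a short, favourable support duration, with about half of the infants cut off by the primary event. That much rests on the text and the planned rates.

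The size does not. The span from about 0% to about 30% of trials favouring aerosol, at identical true benefit on instillation, shows sensitivity to assumed exponential times that are the same in both arms. It is not an estimate of bias. The earlier-rescue results run from about 8% to 94% depending on the assumption and show only that the rule can reward worsening.

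The air-leak windows are a minor mismatch of unknown effect. The primary endpoint, sample size, oxygen level or change, Kaplan-Meier oxygen duration and death or BPD are unaffected.

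**What to change.** In 4.1, 7.2 item 2(b) and 9.1, choose one:

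- **Count support in everyone.** Analyse hours of positive-pressure support, including mechanical ventilation, from randomization to 72 hours of age regardless of instillation, with a stated rule for death. Downside: it includes the effect of rescue surfactant and may dilute the difference.
- **Keep the window and rank instilled infants worst.** Downside: it largely repeats the primary endpoint.

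Keep the pre-instillation summaries, including FiO2 level and change, as they are for objective (b).

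Separately, reconcile 4.1(c) and 9.1 with 7.1 item 4 and 7.2 item 4 on one window that counts air leaks and hemorrhages regardless of instillation.

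The cost is wording, with no new data for the duration measure: case report form item 4 records support for all patients to 72 hours of age, and the data sheet logs setting changes to 96 hours from birth. For air leaks, the outcome fields are coded at days 4, 8 and 29 or discharge without clock times, so a 72-hour cut would need imaging days or progress notes.

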Randomization: Subjects will be randomized to the intervention or active control arm in a 1:1 fashion using a stratified permuted block randomization scheme with variable block sizes of 2 and 4. Randomization lists will be generated by the study biostatistician which will then be used to create an envelope-based system to be used at the individual study sites. Subjects will be included in primary data analyses according to their randomized assignment irrespective of the treatment actually received (intent-to-treat). Exceptions would include those who withdraw their consent to use any of their data prior to subject evaluation.

Accrual. Subjects will be accrued to the study on a first-come basis. The projected accrual is approximately 80 per month, and therefore recruitment is expected to be complete at most 365 days following the study starting point. Subjects will be followed to hospital discharge or 28 days whichever is shorter so total study duration will be approximately 13 months.

Descriptive analyses. Measured outcome variables will be summarized overall and by relevant demographic and baseline variables. Descriptive statistics such as frequencies and relative frequencies will be computed for all categorical variables. Numeric variables will be summarized using simple descriptive statistics such as the mean, standard deviation and range. A variety of graphical techniques will also be used to display data, ex. histograms, boxplots, scatterplots, etc.

Primary efficacy analyses. The primary efficacy analysis will be performed within each cohort separately and is based on a test for superiority of the experimental treatment relative to active control with regards to intubation rate. An overall assessment of the probability of intubation differences across study sites will be done using the Cochran-Mantel-Haenszel test. A one-sided nominal significance level of 5% will be utilized. Additional analyses will be performed utilizing both cohorts of subjects in order to assess differential treatment effects.

Primary safety analyses. All adverse events will be recorded during the study period and then tabulated at the end of the study.

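### The tested air-leak and pulmonary-hemorrhage endpoint stops counting at instillation, the event aerosol is meant to prevent, so an effective aerosol arm is counted for longer and the comparison leans against it.

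*Combined protocol and SAP*

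**What the plan says.** Section 4.1, secondary endpoint c), is headed as protection from acute lung injury and measured by "incidence of lung air leaks or pulmonary hemorrhage from randomization to 72 hours of age or intubation and surfactant instillation". Section 9.1 (Secondary analyses) repeats that window and names the test: "incidence of lung air leaks or pulmonary hemorrhage from randomization to 72 hours or intubation and surfactant instillation), the Cochran-Mantel-Haenszel test will be used". Section 9.1 also states: "All statistical tests will be one-sided and tested at a 5% nominal significance level".

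Three other places bear on this.

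- **A second window.** Section 7.1 item 4 lists "Comparison of incidence of pulmonary complications of RDS to" usual care, to 7 days. Section 7.2 item 4 is headed "Incidence of pulmonary complications to 7 days of age". Neither stops at instillation and neither names a test. Section 7.2 also adds acute pneumonia.
- **Analysis set.** Section 9.1 (Randomization) says "Subjects will be included in primary data analyses according to their randomized assignment irrespective of the treatment actually received (intent-to-treat"). That sentence covers primary analyses. No denominator is given for the lung-injury endpoint.
- **Planned instillation rates.** Section 9.2: "We assume the intubation probability corresponding to the active control group to be 60" percent, against 48% on aerosol in the uninstilled cohort and 42% in the post-instilled cohort.

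**The concern.** The event that ends counting is the primary outcome, so treatment itself affects how long each arm is counted. If aerosol works as planned, fewer aerosol infants have their count cut short, and they accumulate more countable events at the same underlying hazard. A CMH test on proportions cannot correct for this. In the same paragraph Section 9.1 uses Kaplan-Meier and log-rank methods for duration of oxygen because of censoring, but makes no such provision here.

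The cut-off is also informative. Section 7.2 ties instillation to a continuing need for more than 40% oxygen, so counting ends as an infant gets worse. Injury after instillation is part of what avoiding instillation might prevent, yet it falls outside the tested endpoint. At stake is whether this endpoint can show the protection it is named for.

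**Working it through.** **The plan's own figure.** The documents give no event rate, time to instillation or power for lung injury. The figures that drive the problem are the instillation rates behind the sample size, so I checked those first. For 60% versus 48%, one-sided 5%, 80% power:

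n = [1.645·√(2·0.54·0.46) + 0.842·√(0.24 + 0.2496)]² / 0.12² = 212.2

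The continuity correction gives (212.2/4)·[1 + √(1 + 4/(212.2·0.12))]² = 228.6, hence 229 per group. This matches Section 9.2, and corrected power at 229 is 80.1%, as stated. For 60% versus 42% with 100 per arm, power is 78.0% corrected and 82.0% uncorrected, against a stated figure of about 80%.

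**Counted time per arm.** Mean counted hours = (1 − p)·W + p·T, where:

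- p is the instillation rate (Section 9.2);
- W is hours from randomization to 72 h of age. *Assumption:* 66 h in cohort 1 (entry at 6 h of age) and 60 h in cohort 2 (entry at 12 h). Section 4.5 allows entry up to 12 h and 24 h of age respectively;
- T is mean hours from randomization to instillation among instilled infants. *Assumption:* 5 to 30 h.

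With an equal, constant event hazard in both arms, the ratio of counted times approximates the event ratio seen when there is no true difference.

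| Cohort | T (h) | Usual care (h) | Aerosol (h) | Ratio |
|---|---|---|---|---|
| 1, W = 66 | 5 | 29.4 | 36.7 | 1.25 |
| | 10 | 32.4 | 39.1 | 1.21 |
| | 20 | 38.4 | 43.9 | 1.14 |
| | 30 | 44.4 | 48.7 | 1.10 |
| 2, W = 60 | 5 | 27.0 | 36.9 | 1.37 |
| | 10 | 30.0 | 39.0 | 1.30 |
| | 20 | 36.0 | 43.2 | 1.20 |
| | 30 | 42.0 | 47.4 | 1.13 |

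Example, cohort 1 at T = 10: 0.40·66 + 0.60·10 = 32.4 and 0.52·66 + 0.48·10 = 39.1, so 39.1/32.4 = 1.21. In that scenario a true hazard reduction of 1 − 32.4/39.1 = 17% would look like no effect. In cohort 2 the figure is 1 − 30/39 = 23%.

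**Front-loaded hazard.** Suppose instead that the hazard halves every 12 h (assumption). The share of the full-window hazard accrued by time T is f = (1 − 2^(−T/12))/(1 − 2^(−W/12)), and the ratio is [(1 − p_A) + p_A·f]/[0.40 + 0.60·f]. Over T = 5 to 30 h it runs from 1.16 down to 1.02 in cohort 1 and from 1.24 down to 1.03 in cohort 2.

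**Effect on the test.** Take an assumed 5% full-window risk R, cohort 1, T = 10. The risk accrued by T is e = 1 − 0.95^(10/66) = 0.77%. Counted incidence is (1 − p)·R + p·e:

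- usual care: 0.40·5% + 0.60·0.77% = 2.46%;
- aerosol: 0.52·5% + 0.48·0.77% = 2.97%.

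With 229 per arm that is 229·0.0051 = 1.2 extra counted infants on aerosol. By the normal approximation, the one-sided test for aerosol benefit rejects 2.4% of the time under equal hazards instead of 5%. Over T = 5 to 30 h the artefact is 1.3 to 0.7 infants per arm in cohort 1 and 0.8 to 0.4 in cohort 2 (100 per arm). At 10% risk these roughly double.

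**Two limiting cases.** If instillation rates and timing are the same in both arms, the ratio is 1.00. If events are counted to a fixed age regardless of instillation, the windows are equal, so under equal hazards the ratio is 1.00 and the rejection rate 5%.

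**The case against.** The strongest defence is that lung injury before rescue instillation is a definable outcome. Comparing its incidence between randomized arms, with instillation as a competing event, is a legitimate randomized comparison. It also keeps out events that may be due to instilled surfactant or ventilation. That stands as far as it goes: the test is not invalid for that quantity. But the quantity is a poor measure of protection from acute lung injury, because an arm can score better by instilling sooner.

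Other points stand as limits.

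- **Denominator.** A reader might take it as written that all randomized infants are the denominator. It is inferred: intent-to-treat is stated only for primary analyses, and Section 9.1 leaves detail to an analysis plan still to be developed. Restricting to never-instilled infants would not help, since it selects on a post-randomization outcome.
- **Later events.** A reader might infer that leaks and hemorrhages after instillation are never counted. Sections 7.1 and 7.2 count them to 7 days, and the case report form codes these diagnoses at days 4, 8 and 29 or discharge. They are missing only from the endpoint defined in 4.1 and tested in 9.1.
- **False harm.** A numerical excess on aerosol could appear, but with one-sided tests for benefit the plan would not declare it significant.
- **Size.** Entry age, time to instillation, event risk and hazard shape are not in the documents, and the absolute counts involved are small.

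**Conclusion.** The concern holds for the endpoint as defined in 4.1 c) and tested in 9.1. If aerosol lowers or delays instillation, this secondary comparison is biased against aerosol, and injury after instillation is left out of the tested endpoint. Under an equal, constant hazard and T of 5 to 30 h, the null event ratio is about 1.10 to 1.25 in cohort 1 and 1.13 to 1.37 in cohort 2. Under the front-loaded hazard it is 1.02 to 1.16 and 1.03 to 1.24. The direction was the same in every scenario tried; the size depends on the assumptions.

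The harm is lost power or a hidden benefit. The documents do not support reading this as a route to false claims of benefit, or as a flaw in the primary analysis or sample size. It is worth correcting before analysis, at the level of a secondary endpoint.

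**What to change.** In Sections 4.1 c) and 9.1, remove the stop at instillation. Define the endpoint as air leak or pulmonary hemorrhage in all randomized infants, from randomization to one fixed age, whether or not the infant was instilled, and state that denominator. Either 72 h of age or the 7 days of Sections 7.1 and 7.2 removes the unequal counting. Deleting the phrase alone leaves 72 h, so the age must be chosen and made the same in all four sections, along with whether pneumonia belongs to the endpoint. Keep the center-stratified CMH test. A pre-instillation count may remain as a supportive analysis, with instillation treated as a competing event.

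The cost is a few lines of text. Records are already extracted to 28 days or discharge, and the case report form captures the relevant diagnoses irrespective of instillation. The one drawback is that later events partly reflect instillation or ventilation; in an intent-to-treat comparison that is part of the effect of assignment.

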9. STATISTICS

9.1 Statistical Methods

ONY, Inc., or its designee, will be responsible for (a) data management, (b) reviewing and validating all information in the clinical report forms, (c) statistical analysis, and (d) generation of the clinical study report. A Statistical Analysis Plan (SAP) providing details of statistical analyses performed after completion of the study will be developed. Prior to locking the database, all data editing will be completed and decisions regarding the evaluability of subject data for inclusion in statistical analyses will be made. The rationale for excluding any data from statistical analyses will be prospectively defined, and classification of all or part of a subject's data as non-evaluable will be documented before the database is locked and the statistical analysis is begun. ONY, Inc., or designee will perform the statistical analysis of the data derived from this study. All analyses will be carried out using SAS version 9.4 (or higher) statistical software (Cary, NC).

Statistical design: This study is a randomized, multiple-center clinical trial designed to assess the superiority of the experimental intervention (aerosolized Infasurf) relative to active control (“usual care”) with regards to the incidence of intubation and instillation of liquid surfactant suspension. A total of up to 200 subjects who received instillation of surfactant for RDS in the first hour of life (“the post-instilled cohort”) and up to 458 subjects who did not receive surfactant at birth who develop RDS in the first hours of life (“the uninstalled cohort”) will be enrolled. Treatment assessment will be done for each cohort separately, that is, this study may be thought of as two individual trials under one protocol.

Stratification: The randomization will be stratified by center and patient cohort and significance tests applied in the analyses will be stratified by center.

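### Secondary efficacy endpoints are each tested at one-sided 5% with no stated gate, order or adjustment: about an 11–19% chance per cohort of a false nominal benefit

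*Combined protocol and SAP*

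**What the plan says.** Section 4.1 introduces the secondary endpoints as efficacy measures: "Secondary efficacy endpoints will measure other clinical parameters that are indicative of lung surfactant sufficiency". It lists death and/or BPD, severity, duration and acute lung injury. Section 1.7 calls the trial pivotal.

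The secondary-analyses paragraph of 9.1 assigns a test to three of these four:

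- Severity, by stratified Wilcoxon: "oxygen supplementation and respiratory support measures from randomization to Surfactant Instillation or 72 hours of age, whichever comes first".
- Duration, by stratified log-rank: "outcomes measuring the duration of acute RDS (duration of supplemental oxygen)".
- Lung injury, by Cochran-Mantel-Haenszel: "incidence of lung air leaks or pulmonary hemorrhage from randomization to 72 hours or intubation and surfactant instillation".

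It names no test for death/BPD. It closes with "All statistical tests will be one-sided and tested at a 5% nominal significance level". For the primary test, 9.1 says "A one-sided nominal significance level of 5% will be utilized".

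The secondary paragraph does not itself mention cohorts. That comes from the statistical-design paragraph: "Treatment assessment will be done for each cohort separately, that is, this study may be thought of as two individual trials under one protocol".

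The text contains no hierarchy, no condition on the primary result, no alpha split or adjustment, and no statement that the secondaries are exploratory or supportive. Section 9.1 says that a SAP with further detail will be developed.

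**The concern.** A nominal level is an unadjusted one. Several efficacy tests at 5% each, in each of two cohorts, give several separate chances of a false positive, and the written rule does not limit how a positive one may be used. A cohort that missed on intubation could report a secondary respiratory benefit at the level set for the primary, and nothing in the plan would rule that out.

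What is at stake is how far the secondary p-values can be relied on. The primary test, its power and the futility assessment all rest on intubation alone and are untouched.

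**Working it through.** **Check of the plan's own figure.** The plan gives no error rate for its family of secondary tests. The nearest figure to reproduce is the power in 9.2, which confirms that 5% one-sided is the working level. Inputs: 60% vs 48%, 229 per group, z = 1.645, mean rate 0.54.

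- Null SE = √(2 × 0.54 × 0.46 / 229) = 0.0466
- Alternative SE = √((0.60 × 0.40 + 0.48 × 0.52) / 229) = 0.0462
- Continuity-corrected power = Φ[(0.12 − 1/229 − 1.645 × 0.0466) / 0.0462] = 80.1%, as stated

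For the post-instilled cohort (60% vs 42%, 100 per group) the same formula gives 78.0%, or 82.0% uncorrected, against a stated value of about 80%.

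**Inputs for the error rate.**

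- Level per test: one-sided 0.05 (9.1, secondary analyses).
- Cohorts: two, with different patients, so independent (9.1, statistical design).
- Tests per cohort, k: four is my count (oxygen supplementation, respiratory support, duration, lung injury). Counting severity as one test gives three. Testing death/BPD, or splitting air leak from hemorrhage, gives five.
- Correlation ρ between test statistics within a cohort: not given, so taken over 0 to 0.8.

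**Formulas.** With independent tests, the chance of at least one p < 0.05 favoring aerosol under no effect is w = 1 − 0.95^k within a cohort. With equal correlation ρ,

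w = 1 − E[Φ((1.645 − √ρ U) / √(1 − ρ))^k], with U standard normal.

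Over two independent cohorts the chance is 1 − (1 − w)².

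**Results** (one cohort / both cohorts).

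| k | ρ = 0 | ρ = 0.5 | ρ = 0.8 |
|---|---|---|---|
| 3 | 14.3% / 26.5% | 11.8% / 22.3% | 9.3% / 17.7% |
| 4 | 18.5% / 33.7% | 14.4% / 26.8% | 10.6% / 20.1% |
| 5 | 22.6% / 40.1% | 16.6% / 30.5% | 11.7% / 22.0% |

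For k = 4 and ρ = 0: 1 − 0.95⁴ = 0.185, and 1 − 0.95⁸ = 0.337. Even at ρ = 0.9, four tests give 8.8% within a cohort. The futility looks carry no numerical threshold, so their effect cannot be computed.

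**After the fix.** With a gate and a fixed sequence, a false secondary claim under no effect needs the first secondary test to be falsely significant. That is at most 5% per cohort and 1 − 0.95² = 9.75% over both.

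**Placing death/BPD first.** The documents give no rate. Assume 5–20% in controls and a 20% relative reduction. One-sided power (pooled normal approximation) is then about 13–30% with 229 per group and about 10–18% with 100 per group. A sequence starting there would usually stop there.

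**The case against.** The strongest reply is that this is silence and not a rule. No sentence says secondary claims will be made after a failed primary, a detailed SAP is promised, and the design, power and futility passages rest on intubation alone. No secondary result is named as a criterion of success. This stands in part. A reader might infer that the sponsor means to claim secondary benefits whatever the primary shows; the documents do not say so, and the absence of order and gate is only an absence. But the level is stated and applies to all the tests, so following the text as written gives the error rates above.

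A second reply is that 9.1 treats the cohorts as two trials, so pooling them overstates the problem. That is fair, and the per-cohort figure should lead. It is still two to nearly four times 5% with four tests.

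A third is that the range rests on an assumed count and correlation. That stands too: 11–19% is conditional and not a bound.

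Two further inferences are not supported. One is that a false secondary success is probable; on these figures it is the less likely result. The other is that correlated endpoints or lack of masking raise this chance. Correlation lowers it, and lack of masking is a question of bias that plays no part in the calculation.

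**Conclusion.** The concern holds as a missing multiplicity rule for the secondary efficacy endpoints. With four tests per cohort and no true effect, the chance of at least one nominally significant secondary benefit is about 11–19% within a cohort and 20–34% over both, for correlation from 0.8 to 0. With five tests it is about 12–23% and 22–40%. These figures rest on equal correlation, independent cohorts and my count of the tests.

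A reader might go on to conclude that the trial's main result is compromised. It is not: nothing here touches the primary test or its power. The plan should still be changed, because it calls these efficacy endpoints, tests them at the primary's level in a pivotal trial, and does not limit what may be claimed from them.

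**What to change.** In the secondary-analyses paragraph of 9.1, state for each cohort that:

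1. A secondary efficacy claim is made only if that cohort's primary test is significant.
2. Claims then follow one fixed sequence of single tests, each at the primary level, stopping at the first failure. One named oxygen measure and one named respiratory-support measure are separate steps, because two unordered tests within a single severity step would break the error guarantee.
3. Death/BPD is given a test and a place in the sequence.
4. All other secondary results are reported as estimates with confidence intervals and no efficacy claim.

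The sponsor should choose the order before outcomes are compared between arms, including at the first interim analysis. The order in 4.1 should not be adopted by default: it is a list and not a ranking (two items carry the same letter), and it opens with death/BPD, which has low power under the assumptions above.

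The cost is wording only; sample size, primary test and power are unchanged. The downside is that an endpoint later in the order cannot be claimed once an earlier one fails.
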